5.3. Randomization

This is a non-randomized study. The study has a fixed treatment sequence.

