8.3.2. Statistical Methodology

The primary analysis planned for this study is a mixed effect model that includes treatment as a fixed effect and subject as a random effect. The analysis will be performed on the natural log (ln)-transformed PK parameters (AUC₀₋₁, AUC₀₋₂₄, and C_{max}) and include calculation of

least squared (LS) means and the difference between treatment LS means, as well as their corresponding 90% confidence intervals (CIs). The geometric mean ratios and their 90% CIs of the PK parameter for each treatment comparison will be constructed using the exponentiation of the difference and the CIs from the mixed effect model. The comparisons of interest will be as follows:

- Multiple doses of digoxin coadministered with multiple doses of LOXO-305 versus multiple doses of digoxin alone.
- Multiple doses of digoxin coadministered with a single dose of LOXO-305 versus multiple doses of digoxin alone.

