6. STUDY TREATMENTS

The study treatment names and ordering to be used in the TFLs are presented in Table 1.

Table 1: Presentation of Study Treatments in Safety TFLs

Study Treatment	Order in TFLs
0.25 mg Digoxin Alone	1
200 mg LOXO-305 QD + 0.25 mg digoxin QD	2

OD = once daily; TFL = table, figure, and listing.

All TFLs will be based on actual treatments.

Table 2 shows a list of the PK treatment labels and ordering that will be used in the TFLs.

Table 2: Pharmacokinetic Treatment Labels

Study Treatment Labels	Order in TFLs
0.25 mg Digoxin Alone	1
200 mg LOXO-305 Once + 0.25 mg digoxin QD	2
200 mg LOXO-305 QD + 0.25 mg digoxin QD	3

QD = once daily; TFL = table, figure, and listing.

The study treatment sequence names and ordering to be used in the TFLs are presented in Table 3.

Table 3. Presentation of Study Treatment Sequences in TFLs

Study Treatment Sequence	Order in TFLs
0.25 mg Digoxin BID (D1) / 0.25 mg Digoxin QD (D2-7) / 200 mg LOXO-305 QD + 0.25 mg digoxin QD (D8-D16)	1

BID = twice daily; QD = once daily; TFL = table, figure, and listing.

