8.5.3. Pharmacokinetic Statistical Methodology

A statistical analysis will be conducted to investigate the drug-drug interaction on the PK of the following comparisons:

Plasma PK only

• Multiple doses of digoxin coadministered with a single dose of LOXO-305 versus multiple doses of digoxin alone.

Plasma and urine PK

• Multiple doses of digoxin coadministered with multiple doses of LOXO-305 versus multiple doses of digoxin alone.

The natural log-transformed⁴ PK parameters (AUC_{0-t}, AUC_{tau}, C_{max},Ae_{0-x h} and CL_R) will be analyzed using a mixed effect model.⁵ The model will include actual treatment as a fixed effect, and subject as a random effect.

For each PK parameter separately, the least squares mean (LSM) for each treatment, difference in LSMs between the test and reference treatments, and corresponding 90% confidence interval (CI) will be calculated; these values will then be exponentiated to give the geometric least squares mean, geometric mean ratios, and corresponding 90% CI.

Additionally, the pooled estimate (across all treatments) of the within-subject CV will be calculated, and residual plots will be produced to assess the adequacy of the model(s) fitted.

An example of the SAS code that will be used are as follows:

Mixed Model Analysis

```
proc mixed data = <data in>;
  by parcat1n parcat1 pkday paramn param;
  class trtan usubjid;
  model lpk = trtan / cl residual ddfm = kr2;
  lsmeans trtan / cl pdiff = control('1') alpha = 0.1;
  random intercept / subject = usubjid;
  ods output lsmeans = <data out>;
  ods output diffs = <data out>;
  ods output covparms = <data out>;
```

run;

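### Does the variable pkday in the BY statement of the SAP's example SAS code break the primary PK model?

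*SAP*

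**What the plan says.** SAP 8.5.3 sets out the comparative analysis in words and then prints code.

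- **Model in words.** "The model will include actual treatment as a fixed effect, and subject as a random effect". The model is fitted to each log-transformed PK parameter separately. It yields a least squares mean per treatment, test-minus-reference differences and 90% confidence intervals. Protocol 8.3.2 has the same model, a "mixed effect model that includes treatment as a fixed effect and subject as a random effect".
- **Within-subject variability.** "Additionally, the pooled estimate (across all treatments) of the within-subject CV will be calculated".
- **Comparisons.** The single-dose LOXO-305 comparison is for plasma only. The multiple-dose comparison is listed under "Plasma and urine PK".
- **Code.** It is introduced with "An example of the SAS code that will be used are as follows" and uses placeholder dataset names. Its BY statement is "by parcat1n parcat1 pkday paramn param". Differences are requested against control level 1, with a random intercept per subject.

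SAP 6, Table 2, lists three PK treatments: digoxin alone (order 1), "200 mg LOXO-305 Once + 0.25 mg digoxin QD" (order 2) and once-daily LOXO-305 plus digoxin (order 3). Protocol 5.3 adds: "The study has a fixed treatment sequence".

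**The concern.** The text never mentions splitting the analysis by day, yet the code carries a BY variable whose name suggests a PK day. In a fixed-sequence study, day and treatment are the same factor. A model run separately by study day would see one treatment at a time, so it could give no geometric mean ratio, no interval for a ratio and no within-subject CV. Control level 1 would be absent from the Day 8 and Day 16 groups.

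This is the primary analysis, and the SAP says it takes precedence over the protocol's statistical text. If the printed code cannot run as intended, someone has to repair it. There are two obvious repairs: one joint three-treatment model, or separate pairwise models with the Day 7 records copied into each. They differ in residual variance and degrees of freedom, so an undocumented choice between them could alter the reported intervals.

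**Working it through.** The plan gives no figure to reproduce, because the sample size was chosen without statistical considerations (Protocol 8.1, SAP 5). The check is on the structure of the design.

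**Inputs**

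- Subjects: n = 16, the maximum in Protocol 8.1 and SAP 5, all assumed complete.
- Treatments: three for digoxin in plasma and two for digoxin in urine (SAP 6, Table 2; SAP 8.5.3).
- Days: Day 7 is the steady-state digoxin profile and Day 8 the first coadministration (Protocol 3.3.2). Day 16 is the multiple-dose profile (Protocol 3.3.1). The sampling schedule is blacked out. Day 8 is inferred for the single-dose treatment because LOXO-305 has been given only once on that day.
- Within-subject CV: not in the documents. Assumed 20%, range 10% to 30%.

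**Degrees of freedom** = records − rank of (treatment, subject).

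| Reading | Records | Rank | Contrasts with level 1 | Within-subject df |
|---|---|---|---|---|
| BY study day, one group | 16 | 16 | 0 | 16 − 16 = 0 |
| Two treatments (urine, or a pairwise plasma fit) | 32 | 17 | 1 | 32 − 17 = 15 |
| Three treatments (joint plasma fit) | 48 | 18 | 2 | 48 − 18 = 30 |

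Read as study day, the code yields nothing that the text asks for. Read as a value that is constant within a parameter, the BY variable has no effect: the code gives both plasma contrasts, 30 df and the pooled CV. Read as a label for a comparison set, it gives each contrast with 15 df, but the CV would then come from two treatments at a time.

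**Cost of the pairwise repair**

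With complete data the estimated log difference is the same under both fits, since each takes the difference of treatment means over the same subjects. Only the interval changes.

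Half-width on the log scale = t(0.95, df) × √ln(1 + CV²) × √(2/n)

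- t(0.95, 30) = 1.697 and t(0.95, 15) = 1.753. Ratio 1.753 / 1.697 = 1.033, so 3.3% wider at equal residual SD.
- CV 20%: √ln(1.04) = 0.198 and √(2/16) = 0.354. Half-widths are 0.1188 (30 df) and 0.1227 (15 df).

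| Assumed CV | Joint fit, ratio 1 | Pairwise fit, ratio 1 |
|---|---|---|
| 10% | 0.942 to 1.062 | 0.940 to 1.064 |
| 20% | 0.888 to 1.126 | 0.884 to 1.131 |
| 30% | 0.838 to 1.193 | 0.834 to 1.200 |

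With 12 complete subjects the degrees of freedom are 22 and 11, and the ratio of multipliers is 1.046.

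**The case for a change.** The best case for a change is that it is cheap and settles a real mismatch. One word could be dropped from the code, or pkday could be defined. SAP 1 wants the document final before programming begins, and it requires agreement and reporting only for substantial deviations, so a programmer might correct a BY line without recording it. SAP 10 declares no departure from the protocol's model. The two repairs would also estimate different residual variances, so the 3.3% at equal SD does not bound the difference in a given dataset.

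Part of this stands. The arithmetic under the study-day reading is correct, and the SAP would be tidier with pkday defined or removed. The size of a realised difference in residual variance cannot be obtained from the documents.

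The rest does not carry. That pkday means study day is an inference from its name. It is an analysis-dataset variable, and the other variables in the code (parcat1n, parcat1, paramn, trtan, lpk) are not defined in the SAP either. SAP 8.1 leaves the data to ADaM datasets, and SAP 1 leaves the outputs to a separate shells document; neither is available here. Nor does the text leave the model open in any way that matters: one fit per parameter, a mean for each treatment and a CV pooled across all treatments point to the joint fit. Aligning example code with that text follows the SAP rather than departing from it. Protocol 8.5 has the outputs programmed from the final SAP, peer reviewed by an independent programmer and examined in draft at a dry run.

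**Conclusion.** No change to the plan follows. At worst this is a clerical slip in example code; if pkday is constant within a parameter, it is not a slip at all. The model in SAP 8.5.3 and Protocol 8.3.2 governs and is estimable: 30 within-subject df for plasma and 15 for urine with 16 complete subjects.

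The study-day failure is total and therefore visible: no contrasts appear in the output, so it cannot pass into the report as a biased ratio. The remaining risk is that a programmer chooses pairwise fits. With complete data this leaves the geometric mean ratio unchanged and widens its 90% interval by about 3.3% on the log scale at equal residual SD (4.6% with 12 subjects). The documents contain no no-effect boundary or other decision rule for these intervals, and SAP 8.1 already advises caution because the sample size is not based on power.

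This rests on complete data, on Day 8 being the single-dose profile and, for the illustrative intervals, on assumed CVs of 10% to 30%. The conclusion that the text fixes a workable model does not depend on the CVs.

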8.6. Safety and Tolerability Assessments

8.6.1. Adverse Events

All AEs will be coded using the Medical Dictionary for Regulatory Activities (MedDRA) Version 23.0 (or higher if a new version is issued during the study). All AEs will be assigned a severity grade using National Cancer Common Terminology Criteria for Adverse Events (CTCAE) Version 5.0 (or higher if a new version is issued during the study).

A treatment-emergent adverse event (TEAE) will be defined as an AE that starts during or after the first dose, or starts prior to the first dose and increases in severity after the first dose.

A treatment related TEAE will be defined as a TEAE with a relationship of related to the study treatment (LOXO-305 and digoxin), as determined by the investigator.

The assignment of TEAEs to treatments will be as follows:

- A TEAE occurring during or after Day 1 dosing will be assigned to 0.25 mg digoxin alone.
- A TEAE occurring during or after Day 8 dosing of LOXO-305 will be assigned to 200 mg LOXO-305 QD + 0.25 mg digoxin QD.

All AEs will be listed. In addition to the data recorded in the database, the listings will include derived onset time and duration. Onset time will be calculated from the time of the last associated dose for TEAEs only. Where the last associated dose is referring to the last dose received prior to the start of a TEAE.

The frequency of subjects with TEAEs and the number of TEAEs will be summarized for the following categories:

- TEAEs (overall, serious, leading to discontinuation, and leading to death) by treatment
- TEAEs by severity and treatment
- Treatment-related TEAEs (overall, serious, leading to discontinuation, and leading to death) by treatment
- Treatment-related TEAEs by severity and treatment

The frequency of subjects will be summarized separately for TEAEs and treatment-related TEAEs by the following:

- System organ class, preferred term, and treatment
- Preferred term and treatment

For the AE data the following rules will apply:

• For the derivation of TEAE status: If the start date/time of an AE is incomplete or missing, an AE will be assumed to be a TEAE, unless the incomplete start date/time or the end date/time indicates an AE started prior to the first dose.

- For the derivation of treatment-related TEAE status: If the study treatment relationship for a TEAE is missing, a TEAE will be assumed to be a treatment-related TEAE.
- For the derivation of onset time: If the start date/time of an AE is missing, onset time will not be calculated. If the start date/time of an AE is incomplete, where possible, the minimum possible onset time will be calculated and presented in '≥DD:HH:MM' format (eg, if the date/time of the last dose is 01MAY2019/08:00 and recorded start date/time of an AE is 03MAY2019, then the minimum possible onset time will be calculated by assuming the AE started at the first hour and minute of 03MAY2019 [03MAY2019/00:00], thus will be presented as onset time ≥01:16:00 in the listing).
- For the derivation of duration: If the end date/time of an AE is missing, duration will not be calculated. If the start or end date/time of an AE is incomplete, where possible, the maximum possible duration will be calculated and presented in '≤DD:HH:MM' format (eg, if the start of an AE date/time is 01MAY2019/08:00 and its recorded end date/time is 03MAY2019, then the maximum possible duration will be calculated by assuming the AE ended at the last hour and minute of 03MAY2019 [03MAY2019/23:59], thus will be presented as duration ≤02:15:59 in the listing).
- For the calculation of summary statistics: If a subject experienced multiple TEAEs with the same preferred term for the same treatment, this will be counted as 1 TEAE for that treatment under the maximum severity recorded.

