1.6. Risk Assessment

Subjects in the current study will not receive any health benefit (beyond that of an assessment of their medical status) from participating in the study. The risks of participation are primarily those associated with adverse reactions to the study treatments, although there may

also be some discomfort from collection of blood samples and other study procedures. The dose of LOXO-305 administered in this study is not anticipated to induce any potential risk to subjects participating in this study as the dose does not exceed the highest dose safely administered in first-in-human study or healthy volunteer studies. More information about the known and expected benefits, risks, and reasonably anticipated AEs associated with LOXO-305 may be found in the IB.

There is a potential risk that multiple doses of LOXO-305 may lead to decreases in white blood cells including neutrophils, lymphocytes, monocytes, and eosinophils. Therefore, to mitigate any potential immunosuppressive risks during the ongoing SARS-CoV-2 (COVID-19) pandemic, subjects will remain in the Clinical Research Unit (CRU) for 96 hours postdose (Day 20) to allow for LOXO-305 elimination. In addition, subject's hematology laboratory results will be reviewed prior to discharge from the CRU.

Digoxin is a natural cardiac glycoside indicated for the treatment of congestive heart failure that may also be used to treat atrial fibrillation. Digoxin has a narrow therapeutic window, and clinical toxicity can occur, particularly at plasma levels above the normal therapeutic range. Despite its narrow therapeutic range, digoxin is often used as a probe substrate for P-gp in drug interaction studies as it is not metabolized by CYP450 enzymes; gut bacteria have been shown to inactivate digoxin. Digoxin is a probe substrate for P-gp as listed by the FDA. The half-life of digoxin is approximately 1.5 to 2 days. The dose of digoxin chosen for this study, 0.25 mg, is well characterized. Adverse effects caused by digoxin toxicity are well characterized and easily monitored in the clinical setting, and these effects can be treated if required. To monitor for safety, serum digoxin levels will be measured daily (Days 7 through 15) in a clinical safety laboratory assay. These values are for safety only and will not be used to calculate the PK of digoxin.

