- w. End of Treatment is defined as when the subject is released from the CRU following completion of all assessments through Day 20. Early Termination is defined as when the subject is released from the CRU if the subject terminates the study early. Vital sign measurements, ECG, and abbreviated physical examination results are to be available for review by the Investigator (or designee) prior to subject release from the CRU on Day 20 (EOT) or ET. Clinical laboratory results (for clinical chemistry, hematology, coagulation, and UA) and serum pregnancy test results (female subjects only) are to be available for review by the Investigator (or designee) prior to subject release from the CRU at the EOT visit and prior to subject release from the CRU at the ET visit if available.
- x. To be conducted 7 days (± 2 days) following EOT or ET. End of Study is defined as when the subject is contacted by the CRU for a follow-up phone call 7 days (± 2 days) after the EOT visit or ET visit to determine if any SAE or study drug-related AE has occurred since the EOT or ET visit. All subjects who received LOXO-305 or digoxin (including subjects who are terminated early) will receive a follow-up phone call.

Covance Study: 8456071

y. Denotes predose sample collection only.

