Subjects will be confined at the CRU from the time of Check-in (Day -1) until End of Treatment (EOT) on Day 20 upon completion of all PK and safety assessments or Early Termination (ET) if the subject discontinues. Dosing of digoxin will occur on Days 1 through 16 and dosing of LOXO-305 will occur on Days 8 through 16. A follow-up phone call will occur for all subjects who received at least 1 dose of study drug (including subjects who are terminated early) 7 days (\pm 2 days) after EOT or ET. The duration of participation is expected to be approximately 58 days (Screening through follow-up phone call).

In this study, physical examinations, 12-lead ECGs, vital sign measurements, How Do You Feel? inquiries, clinical chemistry panel, coagulation parameters, hematology panel, urinalysis, safety monitoring of serum digoxin levels, and recording of concomitant medications will be performed at specified times during the study.

[figure not shown]
The AEs and serious adverse events (SAEs) will be collected beginning at informed consent. The AEs will be reported throughout the study (ie, from signing of the ICF until End of Study [EOS], or until ET if the subject discontinues from the study and does not complete a follow-up phone call), either as subject medical history (if the event is reported as beginning prior to signing of the ICF or if the event occurs prior to study drug administration on Day 1 and is

assessed as not related to study procedures by the Investigator [or designee]) or as AEs (if the event occurs after signing of the ICF but prior to study drug administration on Day 1 and is assessed as related to study procedures by the Investigator [or designee], or if the event occurs after study drug administration on Day 1 through EOT or ET regardless of relationship to study drug). From EOT or ET through EOS, only AEs assessed as related to study drug by the Investigator (or designee) are to be reported. All SAEs that develop from the time of ICF signing until EOS (or ET, if the subject discontinues from the study and does not complete a follow-up phone call) are to be reported.

Study completion is defined as the time of the last subject's follow-up phone call.

A schematic of the study design is presented in Figure 1.

Figure 1: Study Design

BID = Twice daily; QD = Once daily; EOT=End of treatment; ET= Early termination

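### Crude by-treatment TEAE frequencies compare 7 days on digoxin alone with 12 days to EOT, plus a restricted follow-up, on LOXO-305 + digoxin, with no stated window end and no adjustment for observation time

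*SAP*

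**What the plan says.** SAP 8.6.1 has two attribution rules. For the first period: "A TEAE occurring during or after Day 1 dosing will be assigned to 0.25 mg digoxin alone". For the second: "A TEAE occurring during or after Day 8 dosing of LOXO-305 will be assigned to" the LOXO-305 + digoxin group. Neither rule states an end. Read literally they overlap from Day 8 onward; the sensible reading is that an event goes to the treatment most recently started. SAP Table 1 provides only these two columns for safety output, so there is no post-dosing column.

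The calendar is in SAP Section 4: "Dosing of digoxin will occur on Days 1 through 16 and dosing of LOXO-305 will occur on Days 8 through 16". Subjects stay in the unit "until End of Treatment (EOT) on Day 20 upon completion of all PK and safety assessments", and Protocol 1.6 places that point at 96 hours after the final dose. The protocol schedule (Appendix 4, footnote x) sets the follow-up call: "To be conducted 7 days (± 2 days) following EOT or ET". Collection narrows in that interval: "From EOT or ET through EOS, only AEs assessed as related to study drug by the Investigator (or designee) are to be reported". SAEs continue to be collected whatever their cause.

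SAP 8.6.1 then summarizes the number of subjects with TEAEs and the number of TEAEs by treatment, for all TEAEs and for treatment-related ones. The SAP text contains no subject-time, exposure-adjusted rate, equal-length window or post-dosing category. SAP 8.6.6 plans no inferential safety analysis.

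**The concern.** A reader of the by-treatment TEAE table will naturally compare the two columns. They cover different lengths of time, and because every subject follows the same sequence, the longer window always falls on the combination. Part of any difference may therefore come from longer observation rather than from LOXO-305. Some events in the combination column will also have started after both drugs were stopped.

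The secondary objective is the safety and tolerability of LOXO-305 given with digoxin. With no formal safety analysis planned, the descriptive AE summaries are a principal source for that objective, and nothing else in the SAP corrects the AE comparison for observation time.

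**Working it through.** The documents give no observation time per treatment and no expected AE count, so there is no planned figure to reproduce.

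**Windows for a subject who completes**
- Digoxin alone: Day 1 dose to Day 8 dose = 8 − 1 = 7 days.
- Combination to EOT: Day 8 dose to Day 20 = 20 − 8 = 12 days. Of these, 20 − 16 = 4 days (96 hours) follow the last dose.
- Combination to the call, for related AEs and SAEs only: 12 + 5 to 12 + 9 = 17 to 21 days.
- Subject-days with 16 completers: 16 × 7 = 112 on digoxin alone and 16 × 12 = 192 on the combination to EOT.

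**Expected events to EOT, no LOXO-305 effect, constant daily rate**
- Ratio of expected counts = 192/112 = 12/7 = 1.71.
- Subject incidence, assuming 20% on digoxin alone: 1 − (1 − 0.20)^(12/7) = 0.318, or 32% on the combination.

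**Range over plausible rates.** The documents give no background rate for this study. Two earlier multiple-dose LOXO-305 studies in Protocol 1.4 and 1.4.1 give illustrative values, if their AEs are taken to have arisen over the dosing days: LOXO-BTK-20008, 7/(15 × 13) = 0.036 per subject-day; LOXO-BTK-20016, 11/(16 × 11) = 0.0625. The values 0.01 and 0.10 are assumed, to widen the range. Expected events = rate × 16 × days; subject incidence = 1 − exp(−rate × days). The last column is the probability that one independent Poisson count exceeds the other.

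| Rate per subject-day | Expected events, 7 d vs 12 d | Subjects with a TEAE | P(more events on combination) |
|---|---|---|---|
| 0.01 | 1.1 vs 1.9 | 7% vs 11% | 0.56 |
| 0.036 | 4.0 vs 6.9 | 22% vs 35% | 0.77 |
| 0.0625 | 7.0 vs 12.0 | 35% vs 53% | 0.85 |
| 0.10 | 11.2 vs 19.2 | 50% vs 70% | 0.92 |

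**What shrinks the excess**
- Withdrawals: if 25% of subjects left on Day 12 (4 days into the combination), mean combination time is 0.75 × 12 + 0.25 × 4 = 10 days and the ratio is 10/7 = 1.43.
- A falling background rate: with exponential decline at rate k from Day 1, the expected counts are equal when exp(−7k) − exp(−19k) = 1 − exp(−7k), which corresponds to a half-life of about 11.9 days. With a faster decline the expected excess reverses.
- SAP 8.6.1 counts repeats of one preferred term within a treatment once, which lowers the event ratio.

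**Effect of the proposed rate.** At 0.0625 per subject-day, 7.0/112 = 12.0/192 = 6.25 per 100 subject-days, so the null ratio returns to 1.00.

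**The case against.** The strongest reply is that the excess is conditional. The documents do not give a background AE rate, and a front-loaded one is plausible because Day 1 brings both the start of confinement and the loading dose. With 16 subjects, chance alone will often hide or reverse an expected excess. That stands: a reader might infer that the table is bound to show more events on the combination even if LOXO-305 does nothing, and the documents do not support that.

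A second tempting inference is that treatment-related TEAEs are hit hardest, by 17/7 to 21/7 = 2.4 to 3.0 times, because related events are collected through to the call. This would need an unchanged rate of related events until 9 to 13 days after the last dose. Protocol 1.6 gives a digoxin half-life of about 1.5 to 2 days, and Protocol Appendix 1 ties relatedness to a time course consistent with a causal relationship. If, instead, related risk declined with digoxin from 24 hours after the last dose, the effective combination window would be about 9 + 1.5/ln 2 to 9 + 2/ln 2 = 11.2 to 11.9 days, a ratio of 1.6 to 1.7. Ascertainment also drops from daily inquiry in the unit to one call. The size of any further imbalance from follow-up is therefore unknown.

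It can also be said that the objective states no contrast with digoxin alone, that laboratory, vital-sign and ECG summaries are by timepoint and so unaffected, that AE listings carry onset time from the last dose, and that the table shells are a separate document not seen here. All true, and they limit the importance of the point. But the SAP does tabulate TEAEs by treatment, and listed onset times do not correct that summary.

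**Conclusion.** The point holds in a limited form. The windows are 7 days against 12 days to EOT, with a restricted extension to the call, and the SAP neither states where they end nor accounts for the difference. Under a constant background rate, no LOXO-305 effect and full completion, about 1.7 times as many TEAEs are expected on the combination to EOT. That is an expectation under those assumptions, not a prediction of what the table will show. No separate figure for related TEAEs in follow-up can be defended.

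The consequence is confined to a descriptive secondary safety summary. It is worth correcting before database lock.

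**What to change.** In SAP 8.6.1 and the table shells:

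1. State the end of each window: digoxin alone ends at the Day 8 LOXO-305 dose, and the combination window has a named end (EOT, with follow-up identified separately). This also removes the literal overlap of the two rules.
2. Keep the crude frequencies. Beside them show subject-days at risk and TEAEs per 100 subject-days for each treatment, with all TEAEs counted to EOT.
3. Within the combination total, add a supplementary breakdown of events with onset after the dosing period and events in follow-up. They should stay in the total: Protocol 1.6 holds subjects "for 96 hours postdose (Day 20) to allow for LOXO-305 elimination", so moving early post-dose events out of the combination altogether could under-attribute them and hide delayed effects.
4. Optionally, add a supplementary table of Days 1-7 against Days 8-14. It matches window length but omits Days 15 and 16, when LOXO-305 has been given longest, so it should not replace the main table.
5. Add a footnote that rates remove the effect of window length but not the confounding of treatment with time in a fixed sequence.

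The cost is SAP and shell wording and a few rows or one extra table. Dose times are already recorded in the eCRF (Protocol 5.2), and SAP 8.6.1 already derives AE onset time from the last dose.
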